3.1.1.3 Imputation of adverse event / concomitant medication stop date

Missing stop dates (where in eCRF UN, UNK and 0000 indicate unknown or missing Day, Month and Year respectively for partial missing dates, while completely missing dates would be left empty):

- Completely missing dates will not be imputed.

Partial missing AE/CM end dates are imputed as below:

- If the AE/CM is not ongoing and if only the day is missing: Assume the last day of the collected month.
- If the AE/CM is not ongoing and the month is missing: Assume 31-DEC-YYYY (of the collected year).

After applying these rules, if the imputed AE or concomitant medication (CM) stop date is after the date of death (or after the date of the end of the study), the imputed stop date will be the same as the date of death (or the date of the end of the study).

- If the AE/CM is ongoing, the stop date will remain missing. Completely missing dates will not be imputed.

3.1.2 Baseline definition and analysis visit windows

Baseline is defined as the last evaluable non-missing assessment prior to the start of IP and any information taken after first dose of IP will be regarded as post-baseline information. For CTA parameters additional rules apply related to matching evaluable segments, please refer to CTA imaging guidance document (Version 4.0). If two or more assessments are equally eligible to assess subject status at baseline (i.e. on the same date prior to first dose with no time recorded to distinguish the assessments), the average should be taken as the baseline value. For non-numeric assessments where taking an average is not possible then the best category for ordinal data and the last measurement for non-ordinal categorical data would be taken as baseline as this is the most conservative. In the scenario where there are two assessments on Day 1/Visit 3,

one with time recorded and the other without time recorded, the one with time recorded would be selected as baseline, assuming it could be determined that it occurred prior to first dose. If the assessment is collected on Day 1 but it cannot be determined if it was done before or after the first dose of IP (due to missing time and/or planned time point), then it will be considered as collected after the first dose of IP except if as per protocol the measurement at day 1 is planned to be done before the first dose of IP. If no value exists before the first dose of IP, then the baseline value will be treated as missing.

For analysis visit post baseline for CTA, if more than one measurement falls in the same visit window but in different days, the latest will be used. If several measurements are collected within the same distance from the scheduled study day, the data of the latest visit after the scheduled study day within that window is used. If several measurements are collected during the selected day, the average (for numeric values)/worst (for categorical values) of the measurements is taken. If there are several categorical values corresponding to the worst case, then the last measurement registered in CRF will be taken.

The date of first dose of study treatment will be considered relative Day 1/Visit 3, and the day before the first dose of study treatment will be relative Day -1. Relative days will be calculated as follows only when the full assessment date is known (i.e., partial dates will have missing relative days):

For days on or after the first dose of study treatment: date of assessment - date of first dose of study treatment + 1.

For days before the first dose of study treatment: date of assessment - date of first dose of study treatment.

For the purpose of the statistical analysis, efficacy and safety variables are allocated to the analysis visit as reported in the table below. Analysis visit is defined based on analysis day the visit occurred, visit window reported below, and using scheduled or unscheduled eCRF visits. The allocation to analysis visit windows is performed after the imputation of date of first and last doses of IP as in Section 3.1.1. Measurements with missing or partially missing dates cannot be imputed to any analysis visit.

Table 3 Scheduled analysis visit windows

Analysis visit	CSP visit name		Visit window (days)	
	After amendment 2 ^d	Before amendment 2	CTA – ECHO – Biomarkers ^a	Other parameters
Pre-treatment	Visit 2 – Visit 3		<= 1 ^b	
Day 10	Visit 4		CCI : 3 -17	3 -17
Day 29	Visit 5		Biomarkers: 21 – 37	21 – 37
Day 57	Visit 6		CCI : 49 – 65	49 – 65
Day 85	Visit 7		Biomarkers: 77 – 93	77 – 93
Day 113	Visit 8		Biomarkers: 105 – 121	105 – 121 ^c
Day 122	Visit 9		CTA: 114 – 140 CCI and biomarkers: 118-126	118 – 126
Day 141	Visit 9	Visit 10	CCI : 133 - 149	133 - 149
Day 169	Visit 10	Visit 11	CCI : 161 - 177	161 - 177
Day 197	Visit 11	Visit 12		188 - 206
Day 225	Visit 12	Visit 13	Biomarkers: 217 - 233	217 - 233
Day 253	Visit 13	Visit 14	CCI : 249-264 Biomarkers except CCI : 249 - 285 CTA, ECHO: 234 - 326	244 - 271
Day 325/405	Visit 14	Visit 16	CCI : 317 - 333/ 394 - 416	317 - 333/ 394 - 416

^a CCI , NT-proBNP, CCI CCI NT-proBNP, we will include analysis visits of pre-treatment, Day 113 and Day 253. CCI we will include analysis visits of pre-treatment, Day 10, Day 29, Day 57, Day 113, and Day 253.

^b Includes all measurements collected before or on day 1 prior to first dose of IP. If measurement is done on day 1 but time of collection is missing and per CSP parameter should be collected before first dose of study, analysis phase is “Pre-treatment”.

^c to avoid conflict between analysis visit Day 113 and Day 122, for participants who performed visit 8 before amendment 2 the visit window will be 109 – 117. For participants with missing date of reconsent for amendment 2 or who did Visit 8 before 25Jan2022 (Date of migration in EDC) the visit window will be also 109 – 117.

^d Some scheduled visits were removed after the protocol amendment 2 but these analysis visits will be included in the analysis because they fall in the analysis windows defined before the protocol amendment 2. Please check the latest version of the protocol for more details.

End of Treatment is defined as the last value in the on-treatment phase as defined in section 3.1.3.

Baseline visit window will be derived for the analysis purpose and includes measurements collected prior day 1 or at day 1 prior to the first dose of study treatment.

An analysis visit is classified as scheduled if it was requested per the Schedule of Activity at the time the patient did the visit (especially if visit done before or after protocol amendment 2). Except otherwise specified, the data being assigned as unscheduled analysis visits will not be summarized in tables or presented in figures but only displayed in listings.

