Randomization to the CCI dose group was removed.	
• To reduce the overall sample size of the study• The current number of participants in the [REDACTED] mg dose group is expected to provide sufficient dose-response information on the PK-PD relationship and endpoints, and is unlikely to be the dose with the optimal clinical risk-benefit balance.	Section 1.1 Synopsis; Section 1.2 Schema; Section 4.1 Overall Design; Section 4.3 Justification for Dose; Section 6.1 Study Interventions Administered, Table 8 Investigational Products; Section 6.2.3 Dose Preparation Steps, Table 9 Dose Preparation for Fixed SC Doses of CCI [REDACTED] and CCI [REDACTED] mg MEDI6570 and Placebo; Section 6.3.1 Randomization Procedure; Section 6.3.2 Blinding Procedure; Section 6.3.3 Unblinding for Interim Analysis Purposes (section deleted); Section 9.2 Sample Size Determination; Section 9.5 Interim Analyses

Table 1 Substantial Changes to the Protocol

Description of Change	Brief Rationale	Sections Affected
The number of participants was reduced from 792 to 400. CC1 	To reduce the overall sample size and improve feasibility of completion while maintaining acceptable power to inform development program decisions	Section 1.1 Synopsis; Section 1.2 Schema; Section 4.1 Overall Design; Section 9.2 Sample Size Determination
The 2 formal interim analyses were removed.	The interim analyses were administrative in nature. The full study results will be used for decision making on future development options. The study was designed to continue to completion regardless of the results of the interim analyses.	Section 1.1 Synopsis; Section 1.2 Schema; Section 4.1 Overall Design; Section 6.3.3 Unblinding for Interim Analysis Purposes (section deleted); Section 9.4.1 General Considerations; Section 9.5 Interim Analyses
The Day 405 visit (formerly Visit 16) was removed and the Day 325 visit (Visit 14) (formerly Day 334 [Visit 15]) is the new End of Study Visit	The safety follow-up visit will be performed approximately 3 months after the last dose (shortened from 6 months). CC1 	Section 1.1 Synopsis; Section 1.3 Schedules of Activities, Table 5 Schedule of Activities: Follow-up Period; Section 4.1 Overall Design

Table 1 Substantial Changes to the Protocol

Description of Change	Brief Rationale	Sections Affected

 • CCI [REDACTED] • [REDACTED] • [REDACTED] • [REDACTED] 		

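### SAP Table 3 omits the pre-Amendment 2 Visit 15 (Day 334), so a Visit 15 done on its nominal day or later has no row in the by-visit summaries

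*SAP*

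**What the plan says.** The protocol's summary of changes for Amendment 2 (Table 1) states that "the Day 325 visit (Visit 14) (formerly Day 334 [Visit 15]) is the new End of Study Visit". It also says that the Day 405 visit, formerly Visit 16, was removed. The current protocol therefore has one visit after Day 253, at Day 325 ± 7 days (Table 5). The superseded schedule had two, at Day 334 and Day 405.

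SAP section 3.1.2 sets the allocation rule: "Analysis visit is defined based on analysis day the visit occurred, visit window reported below, and using scheduled or unscheduled eCRF visits". Table 3 gives the windows, with separate columns for visit numbers after and before Amendment 2. Its last row reads "Day 325/405 Visit 14 Visit 16", with windows "317 - 333/ 394 - 416" both for the redacted biomarker and for the other parameters. The before-amendment column names Visits 10 to 14 and then Visit 16.

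Three further rules in section 3.1.2 matter:

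- Table 3, footnote d, keeps visits that Amendment 2 removed, on the ground that they fall in a window.
- An analysis visit counts as scheduled if the Schedule of Activities in force at the time required it.
- Otherwise, "the data being assigned as unscheduled analysis visits will not be summarized in tables or presented in figures but only displayed in listings".

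**The concern.** Table 3 sets out to place visits made under the old schedule, and it does so for Day 122 and Day 405. For Day 334 it has neither a visit name nor a window that contains the day. By the SAP's own test a Visit 15 made under the old schedule was scheduled and should be summarised, but the day-based rule gives it nowhere to go.

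The result also depends on when the visit took place. An early Visit 15 enters the Day 325 row, and an on-time or late one enters no row. The tables exposed are the by-visit descriptive summaries of whatever Visit 15 collected, possibly PK, ADA, laboratory values, vital signs and the redacted biomarker. These would be off-drug values, taken 334 − 225 = 109 days after the scheduled last dose.

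**Working it through.** **Inputs.** Window bounds are from SAP Table 3. The old Visit 15 day is from the protocol's Amendment 2 change table, used only to identify the superseded visit. Dates: Amendment 1, 10 March 2021, and Amendment 2, 9 November 2021 (protocol). The migration date in the data capture system, 25 January 2022, is from Table 3, footnote c.

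**Step 1: the plan's own window.** 325 ± 8 = 317–333, as printed. The current visit tolerance, 325 ± 7 = 318–332, lies wholly inside it, so visits on the Amendment 2 schedule are covered.

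**Step 2: Day 334 against every window that could hold it.**

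| Table 3 window | Days | Contains Day 334? |
|---|---|---|
| Day 253, other parameters | 244–271 | No |
| Day 253, biomarkers ("Biomarkers except CCI : 249 - 285") | 249–285 | No |
| Day 253, imaging ("CTA, ECHO: 234 - 326") | 234–326 | No |
| Day 325 | 317–333 | No, by one day |
| Day 405 | 394–416 | No |

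Days 334 to 393 are unassigned for every parameter: 393 − 334 + 1 = 60 days.

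**Step 3: no other rule recovers it.** Allocation is by study day, and the SAP's version 3.0 change list records that use of nominal eCRF visits was dropped. Footnote d helps only visits that fall in a window. The PK and ADA time points in SAP sections 3.3.3.1 and 3.3.3.2 also pass from Day 253 to Day 325/405.

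**Step 4: which Visit 15 dates are lost.** The old tolerance is not in the documents, so it is varied here. For a tolerance of ±h days (h up to 17), the days from 334 to 334 + h are lost: h + 1 of the 2h + 1 permitted days.

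| Assumed tolerance | Permitted days | Pooled as Day 325 | No analysis visit |
|---|---|---|---|
| ±3 | 331–337 (7) | 331–333 (3) | 334–337 (4) |
| ±7 | 327–341 (15) | 327–333 (7) | 334–341 (8) |
| ±11 | 323–345 (23) | 323–333 (11) | 334–345 (12) |

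These are counts of calendar days, not of participants.

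**Step 5: who could have had a Visit 15.** Day 1 is the first dose, so Day 334 is first dose + 333 days.

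- To reach Day 334 by 9 November 2021, first dose by 11 December 2020.
- To reach Day 334 by 25 January 2022, first dose by 26 February 2021.
- A participant first dosed on the date of Amendment 1 reaches Day 325 on 28 January 2022 and Day 334 on 6 February 2022, both after the migration.

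The group is unlikely to be empty. SAP version 1.0 is dated 15 September 2020, and protocol section 9.4 planned it within a month of first dosing. Taking that date as an assumed first dose, Day 334 would be 14 August 2021, before Amendment 2.

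**The case against.** The case against giving this much weight is strong.

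- **The legacy dose group.** A reader might infer that the whole legacy dose group, planned at 27 evaluable participants, loses its post-treatment values, because all of it was randomised before Amendment 2. The dates do not support this. Randomisation to that dose continued under Amendment 1, and anyone first dosed from 10 March 2021 reached Day 325 after the migration. If they had moved to the new schedule, their visit falls inside the window. This point stands in full.
- **Visit 15's content.** The superseded schedule is not in the documents. The absence of Day 334 from the PK and ADA time points fits an oversight, but it also fits a visit without those samples. This stands, so the consequence must be stated conditionally.
- **Loss and bias.** The 8 of 15 days at ±7 might be read as a 53% data loss, or the early/late split as a bias. Neither follows: the share counts days under an assumed tolerance, and nothing in the documents links visit timing to the values measured.
- **Other outputs keep the data.** ADA categories use scheduled and unscheduled samples (SAP 4.2.9.1). PK is plotted individually against actual time and listed (4.2.9.2). Liver-elevation outputs take all measurements, and laboratory shift tables cover only the on-treatment phase (4.2.10.8). Adverse events go by phase (3.3.5.1), and ECG is only listed (4.2.10.10). Participants who stayed on the old schedule also had Day 405, which has its own window. All of this stands.

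None of these points gives Day 334 a row. They limit the consequence but leave the gap in the table.

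**Conclusion.** The gap is real and visible in the current SAP: Visit 15 is unnamed, and its nominal day lies one day outside the nearest window. Followed as written, the SAP leaves an on-time or late Visit 15 out of every by-visit summary and pools an early one as Day 325.

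The effect is limited to descriptive follow-up rows. It concerns an unknown, probably small, subset: mainly participants first dosed by about 26 February 2021, plus any whose site or consent moved late to Amendment 2. The conclusion about exposed data rests on one assumption, that Visit 15 collected at least some of the parameters summarised by visit. The counts of lost days rest on the assumed tolerance. The primary endpoint and all other Day 253 efficacy analyses are untouched. It is worth correcting because the correction is cheap, not because it threatens a main result.

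**What to change.** In SAP Table 3, add Visit 15 to the before-amendment column of the Day 325 row and widen the window from 317–333 to 317–342. This uses the half-width of 8 days found in most of the table's rows, around both nominal days: 325 ± 8 = 317–333 and 334 ± 8 = 326–342. It stays clear of the Day 405 window, which opens at Day 394. Apply it to the parameters summarised by visit: PK, ADA, laboratory values, vital signs and the redacted biomarker. ECG needs no change.

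Check the upper bound against the superseded schedule first. Day 342 covers a tolerance of up to ±8, but ±11 would need Day 345.

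Alternatively, give pre-Amendment 2 participants a separate Day 334 row. The wider window pools values nominally nine days apart (334 − 325), which a footnote should state. A separate row avoids that but may be sparse.

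The cost is one table row, its footnote and the matching programming, with no new data.

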Table 4 Schedule of Activities: Intervention Period

Procedure	Visit:	3	4	5	6	7	8	9	10	11	12	Notes	Details in CSP section or appendix
	Day (± 7): ^a	1	10 ^a	29	57	85	113	141	169	197	225		
Observational period		X		X								Participant must be in clinic for 2 hours after dosing.	Section 8.2.5.2
Assessment of AEs/SAEs		X	X	X	X	X	X	X	X	X	X		Section 8.3
Concomitant medications		X	X	X	X	X	X	X	X	X	X		Section 6.5
Assess for injection site reactions		X		X	X	X	X	X	X	X	X		Section 8.2.5.3

^a The visit window is ± 7 days for dosing visits and ± 3 days for non-dosing visits (ie, Day 10 [Visit 4]). If a participant is dosed outside of the visit window, he or she should return to the initial planned schedule for subsequent visits.

AE, adverse event; CSP, Clinical Study Protocol; CV, cardiovascular; ECG, electrocardiogram; HIV, human immunodeficiency virus; CCI [REDACTED]

NT-proBNP, N-terminal prohormone brain natriuretic peptide; PK, pharmacokinetic(s); SAE serious adverse event; CCI [REDACTED]

Table 5 Schedule of Activities: Follow-up Period

Procedure	Visit:	13	14	Notes	Details in CSP section or appendix
	Day:	253 (- 4 to + 11 days)	325 (± 7 days)		
End of study visit			X		Section 4.3
Full physical examination			X		Section 8.2.1
Weight			X		Section 8.2.1
Vital signs		X	X	Whenever vital signs and blood draws are scheduled for the same nominal time, the blood draws should occur last.	Section 8.2.2

Table 5 Schedule of Activities: Follow-up Period

Procedure	Visit:	13	14	Notes	Details in CSP section or appendix
	Day:	253 (- 4 to + 11 days)	325 (± 7 days)		
ECGs		X	X		Section 8.2.3
Assessment of AEs/SAEs		X	X		Section 8.3
Concomitant medications		X	X		Section 6.5
Collect blood for:					
Clinical safety (clinical chemistry and hematology)		X	X		Section 8.2.4
PK		X	X		Section 8.5.1
CCI		X	X	Sample collected on Day 325 will be stored.	Section 8.6.1
CCI NT-proBNP		X			Section 8.6.1
Circulating biomarkers of inflammation CV disease		X			Section 8.6.1
Immunogenicity		X	X		Section 8.5.2
Creatinine for calculating eGFR		X		should occur within 30 days before the CTA; either local laboratory or point of care testing can be used.	Section 8.2.4
Collect urine for:					
Future use (optional)		X		Sample will be collected and stored.	Section 8.6.2
Echocardiogram		X			Section 8.1.1 and 8.1.2 (including instructions for repeating uninterpretable

Table 5 Schedule of Activities: Follow-up Period

Procedure	Visit:	13	14	Notes	Details in CSP section or appendix

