07MAR2022, v3.0	
Due to visit 9 removed in CSP amendment 2, visit 9 and following visits do not correspond to the same visit according to when patient was randomized. The visit “Day XX/Visit Y” were replaced by “Day XX” in all the SAP and Shells.
 
Variables removed from CSP amendment 2.0 are kept in the Statistical Analysis Plan (SAP) and will be analysed with descriptive statistics only (no statistical model, no figure, no subgroup analysis). Secondary endpoints removed from CSP amendment 2 are analysed as exploratory endpoints.
 
Since interim CTA at Day 122 was removed, only descriptive statistics will be provided at Day 122 for CTA parameters (no statistical model).
 
Everything that concerns interim analyses was removed especially section 5.
 
Analysis visit windows were added, and it was removed that nominal eCRF visits will be used in statistical analyses.
 
The rule for complete/partially missing start and stop dates of concomitant medication was updated.
 
For geometric mean calculation, an imputation rule was added for variables records with zero value.
 
It was added that the description of primary and secondary efficacy parameters will be studied over the course of the study using baseline value. In case of departure from the a priori distribution, the statistical analysis planned in this SAP will be updated.
 
Definitions of change from baseline (normal distribution), relative change from baseline (log-normal distribution) and percent change (any distribution) were added.
 
It was specified “one sided” before “p-value”, also “95% CI” was replaced by “90% CI”.
 
A listing on overdose was added.
 
Following sensitivity analyses were removed: LOCF and MMRM (not appropriate since interim CTA is removed). Sensitivity on patients without CTA assessment changed from baseline to Day 253 was added.
 
Some subgroup removed: CCI subgroup defined on tertiles were removed only medians were kept, repetition of subgroups on patients with reduced ejection fraction.
 
LLOQ value was updated to 0.0328 µg/mL.
 
CCI CCI [REDACTED]
 
Addition that the bioanalytical test site will have access to the randomization list.

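### SAP Table 3 footnote c sets a Day 113 window narrower than the protocol's Visit 8 window, so some on-protocol samples miss the by-visit summaries and some pre-dose samples are filed under Day 122

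*SAP*

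**What the plan says.** Protocol section 1.3, Table 4, makes Visit 8 (Day 113) a dosing visit with PK drawn before the dose. Its footnote a states: "The visit window is ± 7 days for dosing visits and ± 3 days for non-dosing visits".

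SAP section 3.1.2 allocates data by study day: "Analysis visit is defined based on analysis day the visit occurred, visit window reported below, and using scheduled or unscheduled eCRF visits". The SAP amendment history for version 3.0 records that "it was removed that nominal eCRF visits will be used in statistical analyses". The default Day 113 window in Table 3 is 105 to 121 in both columns ("Biomarkers: 105 – 121" in the biomarker column). The Day 122 window, for the Visit 9 that existed before Amendment 2, is 118 to 126 for biomarkers and for other parameters.

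Footnote c is marked only on the Day 113 entry under Other parameters. Its purpose is "to avoid conflict between analysis visit Day 113 and Day 122", and its rule is that "for participants who performed visit 8 before amendment 2 the visit window will be 109 – 117". A second sentence extends the same window: "For participants with missing date of reconsent for amendment 2 or who did Visit 8 before 25Jan2022".

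SAP section 4.2.9.2 summarises PK concentrations by analysis visit. Sections 3.3.3.1, 3.3.3.2 and 3.3.5.2 allocate ADA, PK and laboratory results through Table 3.

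**The concern.** An analysis window should at least contain the days on which the protocol permits the visit. For the footnote c participants it does not. Two things follow.

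- An early but on-protocol Visit 8 has no analysis visit, so its values cannot enter any by-visit table or figure.
- A late but on-protocol Visit 8 is labelled Day 122. That visit was not a dosing visit and nominally came nine days after Dose 5 (122 − 113 = 9), whereas the Visit 8 PK sample is taken before Dose 5. For PK, a secondary endpoint, one summary could then combine concentrations from opposite sides of a dose, or the pre-dose sample could compete with the genuine Visit 9 sample for the same slot.

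Biomarkers have a different problem. The footnote mark is absent there, so the Day 113 and Day 122 windows still overlap, and Day 113 is the only visit between pre-treatment and Day 253 in the NT-proBNP repeated-measures model (Table 3, footnote a).

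**Working it through.** **Inputs.** Visit 8 target Day 113 and tolerance ±7 days (Protocol Table 4, footnote a). From SAP Table 3, Other parameters: Day 85 window 77 to 93 (the biomarker column has the same, "Biomarkers: 77 – 93"); Day 113 window 105 to 121, or 109 to 117 under footnote c; Day 122 window 118 to 126. Dosing days 1, 29, 57, 85, 113 and so on (SAP section 3.4), so the Day 113 dose is the fifth.

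**Step 1: the stated reason for the footnote.** Days lying in both 105–121 and 118–126 are 118, 119, 120 and 121. The conflict is real. A window ending at Day 117 removes it, so the upper cut does what the footnote intends.

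**Step 2: the lower cut.** No other window reaches Days 105 to 108, since the Day 85 window ends at Day 93. Moving the lower bound from 105 to 109 therefore resolves no conflict. A window of 105 to 117 would avoid Day 122 equally well.

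**Step 3: permitted Visit 8 days under footnote c.** 113 − 7 = 106 and 113 + 7 = 120, giving 15 permitted days.

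| Visit 8 on | Analysis visit | Days | Share of permitted days |
|---|---|---|---|
| 106–108 | none | 3 | 3/15 = 20% |
| 109–117 | Day 113 | 9 | 9/15 = 60% |
| 118–120 | Day 122 | 3 | 3/15 = 20% |

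**Step 4: from days to samples.** The documents do not give the spread of actual visit days, so this step is an assumption. Weight each day d from 106 to 120 by exp(−½((d − 113)/SD)²), scale the weights to sum to 1, and add them over 106–108 and over 118–120. By symmetry the two sides are equal.

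| Assumed spread | No analysis visit | Labelled Day 122 |
|---|---|---|
| SD 2 days | 1.1% | 1.1% |
| SD 3 days | 6.1% | 6.1% |
| SD 4 days | 10.6% | 10.6% |
| Uniform | 20% | 20% |

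**Step 5: two samples in one window.** If a late Visit 8 sample and a true Visit 9 sample both fall in 118–126, SAP section 3.1.2 does not clearly say which is used. The rule to take the latest is written for CTA. The following sentence, on equal distances from the scheduled day, only implies that the closest would be chosen.

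**Step 6: biomarkers.** Days 106 to 120 all lie within 105–121, so no on-protocol Visit 8 NT-proBNP value is lost from Day 113. However, a pre-Amendment 2 Visit 9 sample on Days 118 to 121 satisfies both windows, and could therefore also qualify for the Day 113 slot in the model.

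**Step 7: the remedies.** Restoring only the lower bound (105–117) keeps 12 of 15 permitted days under Day 113 and leaves none unassigned, but Days 118 to 120 still go to Day 122. Keeping 105–121 and separating the visits by the Dose 5 date keeps 15 of 15.

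**The case against.** Much of the data survives elsewhere. ADA category outputs include unscheduled measurements (SAP section 4.2.9.1), the liver-test outputs use all measurements (section 4.2.10.8), and individual PK concentrations are listed and plotted against actual time (section 4.2.9.2). PK is descriptive only, with no test. All of this stands and confines the point to by-visit summaries and figures.

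The ±7-day text comes from Amendment 2, while footnote c mainly governs earlier visits. The amendment log calls the text a clarification, so ±7 days earlier is a reasonable assumption, but the superseded schedule is not supplied to prove it.

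SAP section 3.1.2 counts an analysis visit as scheduled only if the schedule in force at the time required it, and otherwise lists the data only. That already keeps most post-Amendment 2 data out of the Day 122 summaries. It does not help those whose schedule included Day 122, who are the main group here.

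A reader might infer that the Day 122 post-dose concentrations will be biased downward, or that a true Visit 9 sample shifted to Days 127 to 129 would be left without a window. The first depends on which sample is selected, which the SAP leaves unclear. The second assumes that Visit 9 was timed from the actual Dose 5 date, which the documents do not state. A reader might also take the missing-reconsent clause to cover everyone first consented under Amendment 2. It more naturally describes earlier enrolees whose status is unknown, though the wording does not exclude the wider reading.

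Moving away from nominal visits was a deliberate change in SAP version 3.0. Separating samples by dose date respects it.

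**Conclusion.** The point holds in a limited form. For the footnote c participants, 6 of 15 protocol-permitted Visit 8 days are either unassigned (106 to 108) or labelled Day 122 (118 to 120), and the lower-bound cut has no purpose. The consequence is incomplete or mixed by-visit summaries and figures of PK, ADA, safety laboratory data and vital signs.

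The 6 in 15 should not be read as 40% of samples lost; that equates days with samples and needs a uniform spread. On the assumed spreads, the share on each side is about 1% (SD 2 days), 6% (SD 3), 11% (SD 4) or 20% (uniform), and the number of participants covered is not given. Nor should it be inferred that the footnote weakens the efficacy analyses. The primary endpoint is CTA-based and unaffected, and the footnote as printed does not apply to NT-proBNP. The NT-proBNP issue is the separate overlap on Days 118 to 121, where the allocation of a pre-Amendment 2 Visit 9 sample is not clearly defined.

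This rests on the ±7-day window having applied before Amendment 2, and on the footnote mark sitting only where Table 3 prints it.

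**What to change.** Amend SAP Table 3 and footnote c as follows.

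- Restore the Day 113 lower bound to 105 for all participants.
- On Days 118 to 121, for all parameters including biomarkers, allocate by the recorded date of Dose 5: a sample at or before Dose 5 goes to Day 113; a sample after Dose 5 goes to Day 122, and only where a pre-Amendment 2 Visit 9 took place.
- State that the missing-reconsent clause does not apply to participants first consented under Amendment 2.

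Dose dates are already recorded in the eCRF (Protocol section 6.4), so no new data are needed. The cost is a few lines of SAP wording and a small programming change.
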